### 4. NLR

The NLR  $((1-\text{sensitivity})/\text{specificity})$  will be computed using the standard formula with two-sided 95% CIs computed using exact 2x2 contingency table methods. A two-sided 95% CI for the NLR  $<1$  and favoring OA will indicate improvement in NLR; the relative NLR will also be computed relative to IUS. The same analysis will be performed for SenoGram versus IUS and versus Imagio (IUS+OA).

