### 1.2 Secondary Objectives

To evaluate the following overall and for individual readers for IUS versus Imagio (OA+IUS):

- the Imagio (IUS+OA) partial Receiver Operator Characteristic (ROC) Area under the Curve (AUC) for 95-99% vs IUS for 95-99% sensitivity
- the sensitivity and specificity for Imagio (IUS+OA) versus IUS according to multiple models for readers and masses used for assessing sources of variation
- the Negative Likelihood Ratio (NLR) for IUS versus Imagio (IUS+OA).
- the Imagio (IUS+OA) downgrades and upgrades relative to IUS, separately, for benign and malignant masses
- the net gain (new True Positives [TP] + new True Negatives [TN] – new False Positives [FP] – new False Negatives [FN]) estimate of Imagio (IUS+OA) versus IUS combining benign and malignant masses
- the usage and performance of the SenoGram model for the purposes of determining whether it will be adjusted prior to starting the pivotal study

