## 2. ENDPOINTS - endpoints to include a separate mammogram analysis

### 2.1 Primary Endpoint

To evaluate the following overall and for individual readers for IUS versus Imagio (IUS+OA):

- the gain in Imagio (IUS+OA) specificity versus IUS for fixed sensitivity (e.g., 98%) with specificities interpolated from the respective ROC curve as applicable.

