### 4. STUDY DESIGN

This will be a single arm, controlled, blinded, multi-reader, multi-case (MRMC) study using a sequential design. The study will include 5-12 readers depending on qualifications and availability.

Imagio (IUS+OA) Training to be completed prior to any reads taking place. Read 1 is immediately followed by Read 2 within the same read session.

- Read 1 (Control): Mammogram (if available) + History + IUS (stills and videos provided), IUS Probability of Malignancy (POM) and BI-RADS scored and the data form locked.
- Read 2 (Test): Mammogram (if available) + History + IUS (stills and videos provided), and Imagio (IUS+OA) (stills and videos provided). An interim IUS POM and BI-RADS is recorded as well as a combined Imagio (IUS+OA) POM and BI-RADS Pre and Post SenoGram on separate data forms.

Read 1 reflects the information available to a radiologist when evaluating standard ultrasound images, taking under consideration the mass and patient history and assessing mammogram results as available. The History details to be provided are summarized under the Blinding section of the protocol. Read 1 (IUS reads) will serve as the control representing current clinical practice. Read 2 (IUS+OA) will be considered the test read and reflect a pre SenoGram IUS and Imagio (IUS+OA) POM and BI-RADS assessment in addition to a post SenoGram IUS and Imagio (IUS +OA) POM and BI-RADS assessment. Following the display of the SenoGram within the Post SenoGram data form, the IUS and OA feature scores are locked, and the reader is prompted to provide a Post SenoGram POM and BI-RADS. Once the Post SenoGram POM and BI-RADS are provided, the form is locked.

A total of 155 complete read sets from the original PIONEER Intention-to Diagnose (ITD) population will be randomly selected from within the PIONEER Study.

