- Comprising the 155 mass read sets, the first cohort will consist of 75 benign and 45 malignant masses (reflecting the same 37.5% prevalence of cancer as for the overall pivotal ITD population), classified by conventional diagnostic ultrasound (CDU) as BI-RADS 3 to 5 to be selected at random in proportion to the original assignment distribution of BI-RADS classifications among subjects in the PIONEER Study. To facilitate the alignment of the PIONEER Pivotal Study data with the Feasibility Study data, the mass image set sampling plan will select a proportion with and without mammograms depending on availability of the mammograms, separately for benign and malignant masses. Cohort 1 will be used for the effectiveness endpoint analyses in support of decision making. The same sampling strategy will be used to ensure a comparable proportion of mass image sets as for the PIONEER Pivotal Study.

- The second cohort consists of 30 additional malignant masses for which 1 or more pivotal study readers scored the mass a false negative during a read from the PIONEER study; this will assess if the excess FN rate observed with OA in the PIONEER study can be reversed.
- The third cohort will consist of five DCIS, lymphoma, or Phyllodes masses; this will assess how these atypical cases will be scored. Since there are so few of these cases, mammogram matching will not be possible.

This evaluation will further achieve the following:

1. The incremental contributions of IUS and Imagio (IUS+OA) by assessing the BI-RADS and POM values at each step in the read order traditionally used in clinical practice.
2. The SenoGram performance versus IUS and versus Imagio (IUS+OA) once IUS + OA features are scored with subset evaluation of the effect of presence or absence of the mammographic data on Senogram performance.

The SenoGram is a classification model that predicts the probability that a lesion is malignant for a given set of reader-assigned feature scores and other relevant data. For this study, the SenoGram will consist of two components, a user interface and a back-end computation engine. The reader will enter feature data into the user interface. When all data has been entered, but prior to a final submission of the data, the user interface will graphically display the model's predicted likelihood of malignancy [not to be confused with POM].

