1.1.7. Effectiveness Analysis

There are no formal tests of hypotheses for this study. P-values that are generated will be regarded as descriptive statistics. IUS+OA pre-is OA before the SenoGram; IUS+OA post is the reader input OA after viewing the SenoGram. The following will be used to assess feasibility of a pivotal study.

Table 1: Effectiveness Analysis for Study Endpoints

Endpoints by Cohort	Analysis/Software
Cohort 1: Primary	

Gain in specificity IUS+OA post vs. IUS at fixed sensitivity (95-99%) interpolated from the ROC AUC curves. This analysis will be repeated for IUS+OA pre vs. IUS and IUS+OA post vs. IUS+OA pre.
 
A recommended pivotal study sample size will be determined using multiple sources, including OR-DBM MRMC sample size program.
 
Review of entire feasibility study report will be used to recommend efficacy endpoints for the pivotal study.
	
OR-DBM MRMC
 
Sample Size: OR-DBM-MRMC Power program, nQuery v7, SAS (PROC POWER), and/or PASS v15.05.

Cohort 1: Secondary	

Partial AUC: Difference (IUS+OA post vs. IUS) in partial ROC AUC curves for 95-99% sensitivity. This analysis will be repeated for IUS+OA pre vs. IUS and IUS+OA post vs. IUS+OA pre.
	
OR-DBM MRMC & methods as per McClish

Specificity and Sensitivity: Observed and model-adjusted specificity and sensitivity will be reported for IUS+OA post vs. IUS using a 2% POM cutoff.
 
These analyses will be repeated for
	
SAS PROC GEE and MIXED treating readers as independent observations and readers as correlated and then readers correlated and masses as independent.

IUS+OA pre vs IUS and IUS+OA post vs IUS+OA pre, and for POM cutoffs of 1%, 3%, 4%, and 5%.
	
Two-sided 95% confidence intervals for sensitivity and specificity will be computed for IUS, IUS+OA pre, the IUS+OA post, and the 3 pairwise differences.

Negative Likelihood Ratios (NLR) for IUS and IUS+OA post, NLR defined as $((1 - \text{observed sensitivity}) / \text{observed specificity})$
	
SAS: Univariate 95% CI for PLR and NLR with variances fit using the logarithmic transformation and the delta method, reference PIONEER Table 14.2.3.2.

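### The NLR improvement rule (Protocol 9.8, item 4) sets its cut-off of 1 on a single modality's NLR and leaves the relative NLR without a criterion

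*Protocol*

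**What the plan says.** The objective is comparative. Protocol section 1.2 lists "the Negative Likelihood Ratio (NLR) for IUS versus Imagio (IUS+OA") among the secondary objectives.

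Protocol section 9.8, item 4 defines the NLR of one modality as (1 − sensitivity)/specificity, "with two-sided 95% CIs computed using exact 2x2 contingency table methods". It then says that an interval for the NLR below 1 "and favoring OA will indicate improvement in NLR; the relative NLR will also be computed relative to IUS". The relative NLR comes in after the semicolon as a further quantity, with no interval, null value or criterion. The item ends by extending the same analysis to the SenoGram against IUS and against Imagio.

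The SAP (section 1.1.7, Table 1) names the quantity as "Negative Likelihood Ratios (NLR) for IUS and IUS+OA post" and the method as "Univariate 95% CI for PLR and NLR with variances fit using the logarithmic transformation and the delta method". It mentions no ratio or difference of NLRs and no rule for improvement.

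**The concern.** A confidence interval supports a comparison only if its null value belongs to the quantity being compared. The value 1 is the right null for the ratio NLR(Imagio)/NLR(IUS). For Imagio's NLR alone, 1 separates an informative test from an uninformative one. IUS, the control, would be expected to lie below 1 as well, so an Imagio interval below 1 does not distinguish the two.

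At stake is a result labelled as improvement on a criterion that does not measure improvement. Protocol section 9.1 bases the move-forward decision on the primary and secondary endpoints taken together in Cohort 1, and NLR is one of the secondary endpoints. Primary objective 1 is to select endpoints for the pivotal study, so the same criterion could be carried forward.

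**Working it through.** **Inputs from the documents.** Cohort 1: "the first cohort will consist of 75 benign and 45 malignant masses" (Protocol section 4). Readers: "The study will include 5-12 readers depending on qualifications and availability" (same section). Target sensitivity: 98%, given as an example in Protocol section 2.1. The documents give no specificity and no correlation between reads. Both are assumed below, with specificity ranging over 10–50%. No error rate or power is stated for the NLR rule, so there is no figure of the plan's own to reproduce.

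**What the cut-off means.** (1 − sens)/spec < 1 if and only if sens + spec > 1. At 98% sensitivity this needs only a specificity above 2%.

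**Worked counts, one reader.** With the SAP's log/delta method, the standard error of log NLR is √(1/FN − 1/45 + 1/TN − 1/75).

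- IUS, 1 FN and 30 TN: NLR = (1/45)/(30/75) = 0.056. SE = √(1 − 0.0222 + 0.0333 − 0.0133) = 0.999, giving a 95% CI of 0.008–0.394. The control's own interval is below 1.
- Imagio, 1 FN and 31 TN: NLR = (1/45)/(31/75) = 0.054, 95% CI 0.008–0.380. The relative NLR is 30/31 = 0.97.

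If favouring OA means a lower point estimate, the second line counts as improvement because of one benign mass.

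**How often the interval condition is met, one reader.** Exact binomial enumeration of P(upper limit < 1). The first figure uses the log/delta interval; the second uses a two-sided Fisher test as a stand-in for the protocol's exact method.

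| Sensitivity / specificity | Log/delta | Exact |
|---|---|---|
| 98% / 40% | 1.000 | 1.000 |
| 98% / 30% | 0.988 | 0.995 |
| 95% / 30% | 0.936 | 0.946 |
| 98% / 20% | 0.674 | 0.886 |
| 98% / 10% | 0.022 | 0.307 |

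**Whole rule under equal true accuracy, one reader.** In paired simulations with sensitivity 94–98%, specificity 30–50% and latent correlation 0.5–0.8, the interval condition is met in about 90–100% of studies. Adding a lower Imagio point estimate brings this to about 37–49%.

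**Whole rule when Imagio is truly worse than IUS at 98%/40%.** These are 2,000 simulated studies per setting, with mass-clustered variance, assumed correlations and no reader-to-reader variation in accuracy.

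| Imagio | True relative NLR | 1 reader | 5 readers | 12 readers |
|---|---|---|---|---|
| 96% / 40% | 2.00 | 24% | 6% | 1% |
| 98% / 30% | 1.33 | 30% | 29% | 23% |
| 95% / 35% | 2.86 | 11% | 1% | 0.1% |

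A second simulation of the first row for one reader puts the figure at about 22–24%.

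**Criterion on the relative NLR, same simulations** (95% CI of NLR(Imagio)/NLR(IUS) below 1; runs with no false negatives in either modality counted as not met).

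| IUS vs Imagio | 1 reader | 5 readers | 12 readers |
|---|---|---|---|
| Equal, 98% / 40% | 0.3% | 2.7% | 4.3% |
| Imagio worse, 96% / 40% vs 98% / 40% | 0.1% | 0.2% | 0.0% |
| Imagio better, 98% / 40% vs 96% / 30% (relative NLR 0.37) | 4.5% | 53% | 88% |

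**Zero cells.** At 98% sensitivity a single reader has no false negatives with probability 0.98^45 = 0.40. The ratio is then zero or undefined.

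**The case against.** The best defence is that the rule is already comparative. An interval for one modality cannot favour OA over anything, and the item closes by describing SenoGram analyses against IUS and against Imagio. If the interval meant is that of the relative NLR, 1 is the correct null and the fault is loose wording. This reading is possible, but the item has just defined the single-modality NLR, and it then brings in the relative NLR as something additional. The SAP, with its separate univariate intervals, does not support the comparative reading either. The ambiguity stands and is itself a reason to rewrite the sentence.

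A reader might infer that the rule is met almost automatically, even when Imagio is no better than IUS or worse. The documents do not support that. The favouring-OA condition is part of the rule. Imagio with 2 FN and 30 TN has NLR 0.111 (0.028–0.443), wholly below 1, but it does not favour OA over an IUS NLR of 0.056, so the full rule would not be met. The near-certain figures belong to the interval condition alone, and they depend on a specificity that the documents do not give. At 10–20% that condition filters more.

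It is also fair to say that the single-reader rates overstate the risk for pooled results. This holds where Imagio loses sensitivity. It holds much less where Imagio loses only specificity (23% even with 12 readers in the setting above).

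Finally, the consequence is modest. The protocol and SAP call all inference descriptive, the SAP carries no improvement rule, and none of the three illustrative move-forward criteria in Protocol section 9.8, item 3 mentions NLR. All of that stands. It limits the damage but does not make the rule correct.

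**Conclusion.** Wrong as written. On its plain reading, item 4 ties improvement to a null value that shows only that Imagio is informative. The comparison with IUS then rests on an undefined phrase. If that phrase means a lower point estimate, the rule is in effect a comparison of two point estimates with no allowance for sampling error. It is met in about 37–49% of single-reader studies with equal true accuracy, and less often when Imagio is truly worse. These rates rest on assumed specificity (30–50%), assumed sensitivity (94–98%) and assumed correlations; the algebra behind the cut-off does not. NLR reaches the move-forward decision only through the general statement that primary and secondary endpoints are weighed together, so this is a correction worth making to a descriptive secondary endpoint, not a threat to the study's main conclusion.

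**What to change.** In Protocol section 9.8, item 4 and in the NLR row of SAP Table 1, replace the rule with wording such as:

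*Improvement in NLR is indicated when the two-sided 95% confidence interval of the relative NLR, NLR(Imagio)/NLR(IUS), lies below 1. NLRs of single modalities are reported as description only.*

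Then:

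- Specify a variance that respects the paired reads of the same masses and the multiple readers. Neither document says how these are handled for NLR.
- Name one interval method, since the protocol (exact 2x2) and the SAP (log/delta) differ.
- State what is done when a modality has no false negatives.
- Apply the same criterion to SenoGram versus IUS and SenoGram versus Imagio.
- Remove or define the favouring-OA condition, which the ratio makes unnecessary.

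The relative NLR is already planned in the protocol, so the cost is a few sentences and somewhat more analysis work for the variance and the zero cells. The downside is that the criterion will be met less often, and seldom for a single reader (4.5% in the simulated setting with a true relative NLR of 0.37). Per-reader results should therefore be shown as estimates with intervals, and any statement about improvement should rest on the pooled analysis.

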### 5. Graphical Displays

The BI-RADS findings for Imagio and SenoGram will be displayed separately for benign masses using three separate scales (0-2%, 2-50%, 50-100%) to better represent reader opinions and Senogram outcomes. The 0-2% scale will be on an expanded scale to allow the readers to more precisely identify the respective POM for Imagio and likelihood of malignancy for the SenoGram.

## **10. DATA COLLECTION AND QUALITY ASSURANCE**

### **10.1 Data Management**

Independent read data for this study is populated in Medidata Rave EDC System via direct data entry during read sessions from readers and read monitor staff. Electronic data collection forms in Rave will be built during study start-up and designed to meet study aims and statistical analysis needs. Electronic case report forms are created based on the study protocol, ACR-CRI scope of work statement, contract, data flows, and data collection needs. The ACR-CRI Data Manager will ensure the eCRFs are tested appropriately, maintain proper version control and all internal and external/Sponsor stakeholders approve the content prior to finalization.

### **10.2 Quality Assurance**

#### **10.2.1 Training**

Reader training will be provided as described in section 5.2 above.

#### **10.2.2 Quality Control**

Monitoring of the readers will be done by ACR in accordance with the procedures outlined under the Reader Study Process Work Flow Section of the protocol and the Independent Review Charter.

#### **10.3.4 Monitoring**

Monitoring methods for assuring data quality for each reader, accurate qualification of each reader and reader responsibilities during the read process will be documented in the Independent Review Charter.

## **11. PARTICIPANT RIGHTS AND CONFIDENTIALITY**

### **11.1 Informed Consent Forms**

Not applicable for this study.

### **11.2 Participant Confidentiality**

Reader sets will be de-identified to maintain PIONEER study participant's confidentiality according to the Health Insurance Portability and Accountability Act (HIPAA), any special data security requirements as stipulated by participating readers, and record retention per the sponsor's requirements.

Any data, forms, reports, video recordings, and other records that the participating reader receives from the sponsor will be identified only by a participant identification number (Participant ID, PID) from the PIONEER study to maintain confidentiality. All records will be kept in a locked file cabinet. All computer entry and networking programs will be done using PIDs only. Information will not be released without written permission of the participant, except as necessary for monitoring by the FDA.

### **11.3 Study Discontinuation**

The study may be discontinued at any time by the sponsor for futility or by FDA, or other government agencies as part of their duties to ensure that research participants are protected.

## 12. PUBLICATION OF RESEARCH FINDINGS

Any presentation, abstract, or manuscript will be made available for review by the sponsor prior to submission.

Study results may be published in support of reimbursement.

Seno will review and approve all manuscripts.

## 14. VERSION HISTORY

Version	Date	Description of Changes
1	27 June 2018	Original protocol
2	24 Sept 2018	
Section 1.1 - Primary Objectives - revised to include
 
 
To select the effectiveness endpoints and determine the corresponding sample size required for the Pivotal study.
 
To evaluate the gain in Imagio (Imagio Internal Ultrasound [IUS] + Opto-acoustic [OA]) specificity versus IUS controlling for sensitivity
 
 
CDU benchmark classification objectives were removed.
 
Section 1.2 - Secondary Objectives- revised to include:
 
 
the Imagio (IUS+OA) partial Receiver Operator Characteristic (ROC) Area under the Curve (AUC) corresponding to the IUS sensitivity over 95-99% sensitivity
 
the sensitivity and specificity for Imagio (IUS+OA) versus IUS according to multiple models for readers and masses used for assessing sources of variation
 
the Negative Likelihood Ratio (NLR) for IUS versus Imagio (IUS+OA).
 
Imagio (IUS+OA) downgrades and upgrades relative to IUS for benign and malignant masses
 
the net gain (new True Positives [TP] + new True Negatives [TN] – new False Positives [FP] – new False Negatives [FN]) estimate of Imagio (IUS+OA) versus IUS combining benign and malignant masses.
 
the usage and performance of the SenoGram model for the purposes of determining whether it will be adjusted prior to starting the pivotal study
 
 
Section 1.3 - Other Objectives- revised to include:
 
To evaluate the following overall and for individual readers for IUS versus Imagio (IUS+OA):
 
 
the differentiation between benign versus malignant masses with respect to Imagio (IUS+OA) feature scores
 
 
Section 1.3 - Other Objectives- revised to include:

Version	Date	Description of Changes
2, cont.	24 Sept 2018	
To evaluate the following overall and for individual readers for IUS versus Imagio (IUS+OA):
 
 
the differentiation between benign versus malignant masses with respect to Imagio (IUS+OA) feature scores
 
 
Section 2.1 - Primary Endpoints - revised endpoints to correspond to objectives
 
Section 2.2 - Secondary Endpoints - revised endpoints to correspond to objectives
 
CDU benchmark classification endpoints were removed.
 
Section 2.3 – Exploratory Endpoints – revised endpoints to correspond to objectives and added mammography endpoint
 
Section 4 – Study Design- modified to sequential design. 5 -10 readers to read both Part 1 and 2 of the study with a minimum 30-day wash-out period in between
 
SenoGram- language added: “When all data has been entered, but prior to a final submission of the data, the user interface will graphically display the model’s predicted likelihood of malignancy [Not to be confused with POM]. The SenoGram figure will also display threshold lines that correspond to estimated sensitivities of 98%, 98.5%, 99%, and 99.5%, in relationship to the boundaries between BI-RADS categories.
 
“Critically, the SenoGram is trained on cases not selected for Cohort 1 of this study”.
 
Section 5.1 Reader Qualification Criteria
 
Removed criteria “ that is at least 70% breast imaging”
 
Added criteria: Ability to participate and read all masses in both IUS and OA/US reader sessions
 
Section 5.2 – Reader Training – revised and re-ordered training sections adding Question and Answer sections
 
Part 4 revised to:
 
Readers reading Part 2 must pass a proficiency test before starting their Imagio (IUS+OA) reads. If this is not achieved the first time the reader takes the test, the reader will be given targeted remediation training to their deviations and a second opportunity to take the test on a different set of test cases. If the reader does not pass the second time, they will be dropped from the study participation and not continue with Part 2 reads. In the case of dropped readers that do not pass the proficiency test or discontinue the study for any other reason (e.g., illness, personal emergency), then the IUS data for those readers will be analyzed separately.

Version	Date	Description of Changes
2, cont.	24 Sept 2018	
Section 6.2 Exclusion criteria
 
Exclusion criteria modified to:
 
 
• Critical missing views for mammogram cases, IUS or OA stills and video that would preclude case from being evaluated by readers
 
 
Section 6.3 Reader Set Selection Criteria
 
The following was added:
 
 
• BBRF will prepare the mass read order for Part 2 of the study.
 
 
Section 7.1 Reader Study Process Work Flow
 
The following language was modified to read:
 
“The images automatically undergo a de-identification process in TRIAD™, whereby all personal identifier DICOM tags in the image metadata are de-identified according to TRIAD™’s anonymization profile. If any personal identifiers are burned into exams received, ACR CRI staff will remove that by pixel cleaning. ACR-CRI imaging technologists will first perform quality control (QC-1) to document an inventory of all exams and their attributes. ACR-CRI contracted multiple mass quality control reviewer will assess the image sets (QC-2) for inclusion by identifying and labeling Mass 1 on all modalities submitted for a given subject case where multiple masses are present. The acceptable image sets from the ACR QC (QC-1 and QC-2) process will be approved by BBRF and considered ready for central read.
 
BBRF will generate the study’s mass randomization scheme for Part 2 of the study. Masses will be randomized separately for Part 1 and Part 2 to keep readers blinded to the fact that they are reading repeat cases. The QC-1 and QC-2 checks will be documented in study specific procedure documents and outputs of such checks documented on study specific forms, all of which will be archived in an electronic Trial Master File (eTMF) and ACR CRI clinical databases.”
 
“BBRF will generate the study’s mass randomization scheme for Part 2 of the study”.
 
Section 7.2 Schedule of Reader Sessions
 
Section 7.2 was modified to accommodate 2 parts to study:
 
Part 1 will include standard reader training on an image viewing workstation, eCRF completion, etc. There will be a minimum 30-day wash-out period in between the reader’s last part 1 read session and the reader’s start of part 2 read sessions.

Version	Date	Description of Changes
2, cont.	24 Sept 2018	
Part 2 will include Imagio (IUS+OA) training and a proficiency test. The same 5-10 study readers from Part 1, will read Part 2. If a reader fails the proficiency test and re-test, they will be dropped from the study at that time.
 
Section 7.3 Description of Reading Environment
 
The first sentence was modified to:
 
After completion of standard training and Imagio (IUS+OA) training (as applicable), each of the readers will use an image display and electronic data capture workstation to perform image analysis, working alongside an ACR Read Monitor, for all reading sessions.
 
Section 7.4 Randomization
 
The following sentence was modified to:
 
BBRF will generate randomized mass list for Part 2 of the study.
 
Section 7.5 Blinding
 
 
• Mammograms (if available) was added
 
 
Section 9 – Statistical Considerations was rewritten to accommodate revised study objectives and endpoints
 
Section 9.1 General Design Issues
 
Modified to accommodate revised objectives and endpoints
 
Section 9.5 Interim Analyses
 
The following sentence was modified to:
 
An interim analysis of the data is planned to follow a completion of a minimum of 72 completed Cohort 1 mass reads by each reader to assess intermediate performance results.
 
Section 9.6 Protocol Deviations
 
The following sentence was modified to:
 
The study data will be evaluated for major and minor protocol deviations. This will be limited to missing and incomplete reads from the Feasibility Study.
 
Artifact reference was removed.
 
Section 9.8 Data Analyses
 
This section was modified to accommodate the revised study objectives and endpoints
 
Multiple formatting and administrative changes were made throughout the document

Version	Date	Description of Changes
3	01Nov2018	
Protocol Cover Page - Indication for Use, modified to:  The Imagio™ breast imaging system is indicated for use by a trained and qualified healthcare provider for evaluation of breasts in women who are referred for a diagnostic breast work-up (including both palpable and non-palpable masses), following clinical presentation, mammography, diagnostic, screening, or staging methodology. In ultrasound mode, the device can be used to assess BI-RADS1-6. For BI-RADS 3-5 lesions, the ultrasound mode should be initially used to assess the lesion before moving to OA. In Opto-Acoustic (OA) mode, the Imagio™ provides information about the central nidus, boundary and peripheral zones to assist in the assessment of BI-RADS category and diagnosis of the benign or malignant lesion(s) of interest. Using OA and the corresponding features of the lesion(s) allows for improved classification of the mass of interest as compared to ultrasound alone in BIRADS 3-5 masses.
 
Section 1.2 Secondary Objectives, modified first bullet to:
 
 
• the Imagio (IUS+OA) partial Receiver Operator Characteristic (ROC) Area under the Curve (AUC) for 95-99% vs IUS for 95-99% sensitivity
 
• Deleted last bullet: the graphical display of BI-RADS 2-3 findings on expanded scales for the purposes of demonstrating Imagio and SenoGram benefit for downgrading benign masses
 
 
Revised : 2. ENDPOINTS - endpoints to include a separate mammogram analysis
 
Section 2.1 Primary Endpoint, modified to: To evaluate the following overall and for individual readers for IUS versus Imagio (IUS+OA)
 
Section 2.2 Secondary Endpoints
 
Item 2 modified to: the Cumulative effect of downgrades and upgrades for combined benign masses and malignant masses
 
Item 3 – Senogram Usage: modified to Sensitivity and specificity discordance with Imagio (IUS+OA)
 
Section 4 Study Design: this section was revised to reflect the changes to the study design.
 
Section 5.1 Reader Qualification: this section was revised to reflect less stringent qualification criteria.
 
Section 5.2 Reader Training:
 
Item 1 – Didactic Training: deleted review of previous studies (PIONEER and MASETRO)

Version	Date	Description of Changes
3, cont.	01Nov2018	
Item 4 – Pass / Fail Criteria: this section was modified to reflect change in pass/fall criteria
 
Section 7.1 Reader Study Process Work Flow, modified third paragraph to: BBRF will generate the study mass randomization scheme for the study.
 
Section 7.2 Schedule of Reader Sessions: this section was revised to reflect the changes in the study design.
 
Section 7.4 Graphical Interface for BI-RADS Category and POM Rating: this section was modified to clarify its usage in the study
 
Section 7.5 Randomization, modified to BBRF will generate the randomized study read list.
 
Section 9.8 Data Analyses, added: item 5 Graphical Displays
 
Multiple formatting changes and typo corrections throughout the document

